10.1. Primary study parameter(s)

This study population consists of one group, where the primary endpoint is defined as the effect of WholeFiber™ for 6 weeks on fecal SCFA levels in surgically treated intermediate to high-risk cutaneous melanoma patients with no concurrent adjuvant treatment. The study is considered to have a positive outcome when paired differences are measured in fecal SCFA levels, comparing pre- and post-intervention. This will be analyzed using a linear mixed-effects model, modeling the fecal SCFA levels post-intervention as the dependent variable and fecal SCFA levels pre-intervention together with patient-specific intercepts and slopes to take paired sampling into account. To further study the role of the gut microbiota, the relationship between post-intervention fecal SCFA levels and gut microbiota composition will be tested using a similar linear mixed-effects model. In this model, the post-intervention fecal SCFA levels will be modeled as the dependent variable and relative abundance of specific bacterial species together with patient-specific intercepts and slopes as independent variables.

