We are planning to conduct this study in patients with a cutaneous melanoma (T3a, T3b, T4a, T4b, N0 or N+, M0, Stage IV with no evidence of M+ disease), that have undergone curative surgical treatment and will not undergo (neo)adjuvant treatment. The product that we are going to use in this trial, WholeFiber™, is hypothesized to influence the microbial composition in a way that specific microbes, which are reported to produce SCFA, are favored on short term^{16,19}. The goal of the study is to test the effect of the inulin rich dietary fiber without any conditions that are hypothesized to influence its effects^{24,25}. The proposed amount of 20 g has been used in previous studies using WholeFiber™, where no adverse effects were reported²⁶.

1.5 Future perspectives: moving towards advanced melanoma treated with immune checkpoint inhibitors

The discovery of the link between the gut microbiome, diet and response to immune checkpoint inhibitors (ICI) in stage IV melanoma patients have shown that the gut microbiome is not only a biomarker for treatment response but can also be a modifiable treatment target^{27,28}. Interestingly, the immune system plays an important role in patients with melanoma tumors.

What is unclear, and in our view should be the first small step and the objective of this study, is to determine whether changes in the gut microbiome in this group of patients (with skin melanoma) is possible at all, if these changes in the gut microbiome lead to an increased production of SCFA and whether the changes in gut microbiome; immune cell composition and SCFA can indeed be measured.

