4.4. Sample size calculation

A sample size calculation was not performed for this study since it is an explorative study. We do not aim to reach statistical significance, paired differences with a 95% confidence interval will suffice to reach the aim of the study. The main aim is to explore the effects of the intervention on our parameters and answer tolerability questions. Since this is an explorative study, inclusion of 20 participants should be sufficient¹⁰.

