8. METHODS

8.1. Study parameters

8.1.1. Main study parameter

Effect of a high fiber prebiotic vegetable (WholeFiber™) for 6 weeks on fecal SCFA levels in intermediate to high-risk cutaneous melanoma patients, with no concurrent adjuvant treatment. HPLC ion chromatography system (Metrohm AG, Herisau, Switzerland) will be used to determine the levels of SCFA. The concentrations of SCFA; butyrate, propionate, and acetate will be measured with a conductivity detector. SCFA will be measured at baseline, halfway intervention and after 6 weeks.

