10. STATISTICAL ANALYSIS

Statistical analyses will be performed using R. In general, continuous data will be presented as mean \pm standard deviation (SD) or median and interquartile range when skewed, and categorical data as counts and percentages. To correctly model the paired pre-post study design, we will use a linear mixed-effects model (*lme4*-package, version 1.1-35.2, Bates et al., 2015). This is performed by adding a patient-specific intercept and slope. As this is an exploratory study, mean differences with a 95% confidence interval will be considered as statistically significant. A false discovery rate (FDR) of 5% will be used in regression analyses, regarding SCFA and bacterial taxa, to correct for multiple testing. We will adjust for differences in age, sex, BMI, and fiber intake before the start of the intervention by including these as independent variables in the linear mixed-effects models described below.

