13. STRUCTURED RISK ANALYSIS

13.1. Potential issues of concern

a. Level of knowledge about mechanism of action

The gut microbiome composition of patients with an immunogenic tumor as an intermediate to high-risk cutaneous melanoma (minimal stage II A) is currently unknown. However, a link between the gut microbiome, diet and response to immune checkpoint inhibitors in melanoma highlights the gut microbiome as a potential biomarker of response to treatment¹. The gut microbiome can be modified through diet, and therefore is a potential therapeutic target.

A higher intake of dietary fiber is linked to positive changes in the gut microbiota and an increase in SCFA-production³⁵⁻³⁹. Dietary fibers can't be metabolized by human enzymes and therefore are fermented in the colon by the gut microbiota, which are able to produce SCFA. Daily intake of 15 g WholeFiberTM for 2 weeks has been shown to greatly modulate the gut microbiota and impact SCFA-production in adults with prediabetes⁷. In our study, we aim to explore the effects of a WholeFiberTM intervention in surgically treated intermediate to high-risk cutaneous melanoma patients, with no concurrent treatment, on fecal SCFA levels and gut microbial composition.

b. Previous exposure of human beings with the test product(s) and/or products with a similar biological mechanism

WholeFiberTM has been tested before in a clinical trial in Dutch adults with prediabetes with positive effects, and a daily dosage of 30 g was well tolerated¹⁶. Currently, WholeFiberTM is under investigation in healthy adults with constipation complaints (HappyFiber study, NL80274.091.22, currently recruiting).

c. Analysis of potential effect

We expect that the WholeFiberTM intervention will greatly modulate the gut microbiota and increase fecal SCFA levels. The gut microbial composition and SCFA production are hypothesized to play an important role as potential therapeutic target for patients with an immunogenic tumor classified as an intermediate to high-risk cutaneous melanoma (minimal stage II A). However, this is an explorative study. If indeed we see these effects, this needs to be further tested in a large randomized controlled trial.

d. Study population

For this study, we will recruit around 20 surgically treated intermediate to high-risk cutaneous melanoma patients, with no concurrent adjuvant treatment.

e. Interaction with other products

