WholeFiberTM is a dried vegetable that is safe for consumption and commercially available. We do not expect an interaction with other products as this is a food product.

f. Predictability of effect

In the previous study of Puhlmann et al. (2022) an increase of +26% in total SCFA levels was measured within two weeks after 15 g/day consumption of WholeFiberTM in adults with prediabetes. Furthermore, a 3-4-fold increase in butyrate-producing bacteria *Anaerostipes* and *Bifidobacterium* was observed. A similar effect can be expected in this study population. No previous studies have been performed before on the effects of WholeFiberTM in a population with cutaneous melanoma patients, however this study aims to explore these effects.

g. Can effects be managed?

Not applicable, WholeFiberTM is a dried vegetable, which is commercially available and proven safe for consumption.

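### The success rule in Protocol section 10.1 counts a fall in fecal SCFA as a positive outcome and does not say which SCFA decide

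*Protocol*

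**What the plan says.** The rule is in Protocol section 10.1: "The study is considered to have a positive outcome when paired differences are measured in fecal SCFA levels, comparing pre- and post-intervention". The same section defines the primary endpoint as the effect on fecal SCFA levels, in the plural, without naming a measure.

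Other sections bear on it:

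- **Which SCFA.** Section 8.1.1 (main study parameter): "The concentrations of SCFA; butyrate, propionate, and acetate will be measured with a conductivity detector". Section 8.3.6 (laboratory method) lists eight acids, including those three. Total SCFA appears only in section 13.1 f, as a result of a previous study: "an increase of +26% in total SCFA levels was measured".
- **Direction.** Section 2 is neutral and speaks of the effect on SCFA levels. Section 1.5 asks "if these changes in the gut microbiome lead to an increased production of SCFA". Section 13.1 c expects that the product "will greatly modulate the gut microbiota and increase fecal SCFA levels", and 13.1 f expects an effect similar to the earlier rise.
- **Criterion.** Section 10 says "mean differences with a 95% confidence interval will be considered as statistically significant" and adds: "A false discovery rate (FDR) of 5% will be used in regression analyses, regarding SCFA and bacterial taxa".
- **Purpose.** Section 4.4 does not aim at significance and says "paired differences with a 95% confidence interval will suffice to reach the aim of the study".

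**The concern.** A protocol need not define success for an exploratory one-arm study. This one does, so the rule should give one clear verdict on any given data set and agree with the study's hypothesis. It falls short in three ways.

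1. A fall in SCFA meets the rule just as a rise does. That contradicts the hypothesis in sections 1.5 and 13.1.
2. With several acids measured, the rule does not say whether a change in one named acid, in any of them or in all of them is needed. The same data can be positive on one reading and not on another.
3. Every estimated mean difference comes with a 95% CI. The sentence in section 10 therefore separates significant from non-significant results only if the reader adds that the interval must exclude zero.

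At stake is the label that the study attaches to its own result. No patient decision depends on it, and section 13.1 c says that any effect seen would need testing in a large randomized trial.

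**Working it through.** The protocol gives no power, SD or sample size calculation, so there is no figure to reproduce. The numbers below only size the consequence. They use paired t-tests, not the mixed model of section 10.1.

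**Inputs.** From the protocol: n = 20 (section 4.4), three acids (8.1.1), 5% FDR (10). Assumed, because the protocol gives none: normally distributed paired changes, equal correlation of 0 to 0.9 between acids, Benjamini-Hochberg as the FDR method, and true rises of 0, 0.3 or 0.5 SD of the paired change. There were 200,000 simulated trials per setting.

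**1. No true effect, any acid significant under the 5% FDR.**

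| Correlation | Positive | With at least one significant fall |
|---|---|---|
| 0 | 5.0% | 2.6% |
| 0.3 | 5.0% | 2.5% |
| 0.5 | 4.8% | 2.4% |
| 0.7 | 4.3% | 2.1% |
| 0.9 | 3.8% | 1.9% |

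The share with a fall is 2.6/5.0 = 52% at correlation 0 and 1.9/3.8 = 50% at 0.9, so about half.

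**2. True rise in all three acids.** With a rise of 0.3 SD and the same FDR rule, a significant fall occurs in only about 0.02-0.06% of trials. Direction then hardly matters.

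**3. Which SCFA decide, when all three truly rise.**

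- *One named acid*, two-sided 95% CI excluding zero: 24.6% at 0.3 SD and 56.4% at 0.5 SD (noncentral t, 19 degrees of freedom).
- *Any acid under the FDR*, correlation 0.9 to 0.3: 22-31% at 0.3 SD and 54-71% at 0.5 SD.
- *All three acids*: Benjamini-Hochberg rejects all three exactly when the largest p-value is at most 0.05. For independent acids this has probability 0.2465³ = 1.5% at 0.3 SD and 0.5645³ = 18.0% at 0.5 SD. At any correlation it cannot exceed the one-acid figure, 24.6% or 56.4%.

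Unless the acids move almost together, the any-acid and all-acid readings can differ widely.

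**4. A rule with one measure and a direction.** If the two-sided 95% CI of one named measure must lie wholly above no change, the chance of a positive verdict under no effect is 0.05/2 = 2.5%, and a fall cannot be labelled positive. With n = 20 the half-width of the interval is t(0.975; 19)/√20 = 0.47 SD of the paired change.

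**5. Can the model in 10.1 give the mean change directly?** It regresses the post-intervention level on the pre-intervention level. Leaving covariates aside, write post = a + b × pre. The mean change is then a + (b − 1) × mean(pre). Neither a nor b alone equals it, so a rule based on the mean change needs a visit term or this derived contrast.

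**The case against.** The strongest reply is that chapter 10 should be read as a whole. Section 10 introduces the models described after it, so 10.1 need not repeat the criterion. The FDR sentence names SCFA regressions expressly and gives multiple testing as its purpose. This stands, and it rules out several stronger readings that a reader might infer:

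- *Any non-zero difference makes the study positive.* The words of 10.1 alone would allow this, but section 10 supplies a significance criterion.
- *False positives are badly inflated.* Accepting any unadjusted CI would give 1 − 0.95³ = 14.3% for three independent acids and 1 − 0.95⁸ = 33.7% for eight. The stated FDR brings this back to about 5% or less.
- *The unadjusted CI and the FDR compete as deciding rules.* For SCFA the FDR is the natural one.
- *Total SCFA is a rival endpoint.* It appears only as an earlier study's result and is never an endpoint of this trial.

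On direction, the objective in section 2 is neutral, any two-sided test splits its false positives evenly, and the sign of the estimate would be reported anyway. This lowers the weight of the point but does not remove it. A neutral objective justifies two-sided estimation; it does not justify calling a fall a positive outcome when a rise is the stated expectation.

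The exploratory label also counts. It argues for having no verdict rule at all, which is one of the two fixes below.

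**Conclusion.** The point holds as a minor one. The success rule in 10.1 requires no increase and does not say whether one, any or all SCFA decide. The significance sentence in section 10 lacks the condition that the interval excludes zero.

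On the natural reading false positives are roughly controlled at about 4-5% under no effect, and about half of these would include a fall that the rule labels positive. If SCFA truly rise, falls are negligible and the remaining problem is which SCFA decide. These sizes rest on paired t-tests with assumed correlations and effect sizes, and should not be read as operating characteristics of the planned mixed model. The gaps in the wording do not depend on them.

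**What to change.** In section 10.1, do one of the following.

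(a) Name one deciding SCFA measure, such as one of the acids in 8.1.1 or their sum, and the mean change from T0 to T2. Say how it is estimated: from a visit term, or from an explicitly derived contrast of the post-on-pre model. Call the study positive only if the two-sided 95% CI for that change lies wholly above no change. Keep the other SCFA as secondary under the 5% FDR.

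(b) Delete the verdict sentence and report estimates with 95% CIs, in line with section 4.4.

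In either case, reword section 10 so that significance refers to *mean differences whose 95% confidence interval excludes zero*.

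The cost is a few sentences, with no new patients, samples or data; (a) also needs the visit term or contrast written into the model description. Under (a), a fall, or a change only in another SCFA, no longer counts as positive. Under (b), the study gives no positive or negative verdict.

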10.2. Secondary study parameter(s)

To analyze changes in gut microbiota in surgically treated intermediate to high-risk cutaneous melanoma patients using WholeFiber™ for 6 weeks, we will use a similar linear mixed-effects model as described above. In this model, the relative abundance of bacterial species post-intervention will be used as the dependent variable and their relative abundance pre-intervention together with patient-specific intercepts and slopes as independent variables. Furthermore, the effect of WholeFiber™ for 6 weeks on the microbial diversity will be evaluated using both alpha and beta diversity metrics. Alpha diversity metrics quantify within sample diversity and can be compared across groups. Beta diversity compares between sample diversity and is often calculated by computing a dissimilarity index (e.g. Bray-Curtis).

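### The primary model in Section 10.1 cannot be run in lme4 as written, and it has no term for the pre-post change that defines a positive outcome

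*Protocol*

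**What the plan says.** Section 10 of the protocol fixes the software (R, lme4) and the random effects meant to represent the paired design: "This is performed by adding a patient-specific intercept and slope". It does not name the slope variable.

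Section 10.1 then sets out the primary model: "modeling the fecal SCFA levels post-intervention as the dependent variable and fecal SCFA levels pre-intervention together with patient-specific intercepts and slopes". A second model in Section 10.1 keeps post-intervention SCFA as the outcome and takes "relative abundance of specific bacterial species together with patient-specific intercepts and slopes as independent variables". Section 10.2 uses post-intervention species abundance as the outcome, with "their relative abundance pre-intervention together with patient-specific intercepts and slopes as independent variables".

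The target is stated separately. Section 10.1: "The study is considered to have a positive outcome when paired differences are measured in fecal SCFA levels, comparing pre- and post-intervention". Section 4.4: "paired differences with a 95% confidence interval will suffice to reach the aim of the study". Section 10: "mean differences with a 95% confidence interval will be considered as statistically significant". On timing, Section 8.1.1 says "SCFA will be measured at baseline, halfway intervention and after 6 weeks", but the models give the mid-trial visit no explicit role. The Section 10 covariates are age, sex, BMI and prior fiber intake; none of them is a visit term.

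**The concern.** There are two separate faults.

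1. **The model asks for more than the layout can supply.** When the post value is the outcome and the pre value a predictor, each patient contributes one row, or two if T1 also counts as post. A patient-specific intercept and slope need more rows per patient than that.
2. **The model does not contain the quantity of interest.** The stated target is a mean paired change, but no term in the model represents visit. The only effect named is the coefficient on the baseline value, which measures how far patients keep their relative position between visits.

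The first fault shows itself when the code is run, so it is not a hidden false positive. The risk lies in the repair. Deleting the random effects is the obvious shortcut. It leaves a post-on-pre regression whose named coefficient can be highly significant when the fiber has done nothing.

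**Working it through.** The protocol gives no computed figure to reproduce here, so the check is structural, supported by simulated data. The version used was lme4 1.1-37; the protocol names 1.1-35.2.

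**Inputs.** 20 patients, one arm (Section 4.4). Two random effects per patient (Section 10). Visits T0, T1 and T2 (Sections 3 and 8.1.1). Outcome and predictor as worded in Sections 10.1 and 10.2. One model per SCFA, which is how the FDR rule in Section 10 reads.

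**Step 1: rows against random effects.** Rows = n × rows per patient; random effects = n × 2. By default lme4 requires more rows than patients, and more rows than random effects.

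| Reading | Rows (n=20) | Random effects | lme4 |
|---|---|---|---|
| T2 on T0 | 20 × 1 = 20 | 40 | stops |
| T1 and T2 on T0 | 20 × 2 = 40 | 40 | stops |
| T0 and T2 stacked, intercept and slope | 20 × 2 = 40 | 40 | stops |
| T0, T1 and T2 stacked, intercept and time slope | 20 × 3 = 60 | 40 | fits |

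The first three readings also stopped at n=200 and n=2000; the two-row readings there have 400 rows against 400 random effects and 4000 against 4000. The one-row reading stops even with a random intercept alone, because rows equal patients. SCFA on species with one row per patient stops in the same way. The reading that fits is not the one Section 10.1 describes.

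The refusal has substance behind it. There are four variance parameters: intercept variance, slope variance, their covariance and the residual variance. With T2 on T0, only 3 of 4 are identified if the slope is on baseline, and 1 of 4 if it is on time. With two rows per patient and a slope on time, 3 of 4 are identified. With three stacked visits all 4 are. If the slope is on baseline and T1 and T2 are both post, the baseline value is constant within a patient, so no patient's own rows carry information about a slope.

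**Step 2: does the named coefficient respond to the effect?** In post = a + b·pre + error, b = cov(pre, post) / var(pre). Adding a constant c to every post value leaves the covariance unchanged, so b is unchanged and only a moves. In one simulated data set b was 0.303 whether the mean change was set to 0, 42.6 or 68.6.

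Proportion significant at n=20 with no true change (200,000 trials per correlation; b tested on 18 df, paired t on 19 df):

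| Assumed T0-T2 correlation | Test of b | Paired t |
|---|---|---|
| 0.2 | 14% | 4.9-5.0% |
| 0.5 | 64% | 4.9-5.0% |
| 0.8 | 99.6% | 4.9-5.0% |

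With an assumed SD of 30, correlation 0.5 and a true shift of 26, b is still significant in 64% of trials, while the paired t rises from 4.9% to 96%. The uncentred intercept is no substitute: with no change (assumed mean 100, SD 30) it was significant in 95% of runs at correlation 0 and 61% at 0.5.

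**Step 3: do the replacements return the target?** In one simulated data set of 20 patients the paired difference was 42.649, SE 10.468, 95% CI 20.7 to 64.6.

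- T0 and T2, visit fixed, random intercept: 42.649 (SE 10.468), the same with the four covariates added.
- Three visits, categorical visit, random intercept and time slope: 42.649 (SE 10.468).
- Three visits, unstructured covariance: 42.649 (SE 10.468).
- Three visits, random intercept alone: 42.649 (SE 7.766). Since 7.766 / 10.468 = 0.74, this SE is 26% too small.

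Type I error of T2 minus T0 at assumed adjacent/end correlations of 0.6/0.6, 0.6/0.5, 0.7/0.49, 0.8/0.5 and 0.8/0.4 was 4.9, 6.7, 9.5, 12.9 and 14.6% for the random intercept alone. For intercept plus time slope with Satterthwaite df it was 4.4, 3.7, 3.8, 3.8 and 3.8% (1,000 trials each, Monte Carlo SE about 0.6 points). These rates serve only to choose between replacements; the protocol proposes neither model in this form.

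**The case against.** The strongest reply is about weight. This is a one-arm exploratory study that disclaims a significance aim in Section 4.4, the error announces itself, and the paired-difference target is already clear. An SAP, not shown here, could carry the correction. All of that is fair, but the protocol itself fixes this model, so an SAP that follows it inherits the fault. Section 10.1 also ties a positive-outcome rule to the analysis.

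On estimability, the refusal comes from lme4's default checks. With them switched off, one-row fits returned output, but in that layout the variance parameters are not all identified, so the output is not usable. Stacking three acids per patient would give 60 rows against 40 random effects and does fit. The protocol does not describe this, the FDR rule points to separate models, and the stacked model would still lack a visit term.

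On the target, a change-score regression with centred baseline does return the mean change through its intercept (about 26 for a true 26 in simulation). The protocol describes neither the centring nor the change score. The 14%, 64% and 99.6% rates apply only if the random effects are deleted and the baseline coefficient is then read as the result. They describe a foreseeable misuse, not a test the protocol proposes.

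On the replacement, three cautions stand. The two-visit model equals the paired t only when the estimated patient variance is above zero. It fell on zero in 19%, 11% and 1% of simulated trials at correlations of 0.2, 0.3 and 0.5, with an SE then about 4-5% smaller; type I error stayed at about 5.2%. The unstructured option needs a package other than lme4. The Section 10 covariates, kept as main effects, do not alter the primary contrast in complete data.

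**Conclusion.** The point holds: the primary model is wrong as written, which is different from leaving detail to an SAP. With one model per SCFA and lme4's default checks, neither the literal reading (20 rows against 40 random effects) nor the generous one (40 against 40) can be run, at any sample size. The same applies to the species models in Sections 10.1 and 10.2. Separately, no named term gives the paired difference that Sections 4.4, 10 and 10.1 set as the target, and the coefficient that is named does not respond to a uniform shift. The row counts and the shift argument need no distributional assumption. The rejection rates rest on simulated data and the stated correlations. This must be corrected before SCFA data are analysed, because otherwise the replacement may be chosen with the results in view.

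**What to change.** Reword Sections 10.1 and 10.2 and the random-effects sentence in Section 10, in an amendment or in the SAP:

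- Make SCFA (and likewise species abundance) at each visit the outcome, with visit as a fixed effect. Remove the baseline value of the outcome as a predictor. State the T2-minus-T0 contrast with its 95% CI as the primary estimate.
- **T0 and T2 only:** patient random intercept, no slope, n−1 df. If the patient variance is estimated at zero, report the paired t interval directly.
- **T0, T1 and T2:** categorical visit with either a random intercept and time slope (possible in lme4) or an unstructured covariance (another package). Use small-sample df: the paired SE tested on 57 df instead of 19 gave 5.9-6.0% type I error. Do not use a random intercept alone with three visits.
- The Section 10 covariates may stay as fixed effects.
- **SCFA on species:** keep the post-intervention question, remove the patient random effects and use ordinary regression with the Section 10 covariates. That is 6 coefficients (intercept, species, age, sex, BMI, fiber intake), so 20 − 6 = 14 residual df.

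No new data or patients are needed. In the two-visit form T1 becomes secondary. In the three-visit intercept-and-slope form, singular fits can be frequent at n=20: 52% of simulated trials when all correlations were 0.6, and near 0% at 0.8/0.5.

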8.3.6. Analyses of fecal material

Collected tubes with feces samples will be stored (at -80°C) until a sufficient batch size is present for further analyses (calprotectin, microbiome, SCFAs). Analyses of the microbiome will be conducted within the UMCG following standardized procedures. The composition and function of the gut microbiome will be analyzed prior to, mid-trial, and after the WholeFiber™ intervention using whole genome sequencing. Temporal changes in the gut microbiome following the WholeFiber™ intervention can be traced up to species and even strain level by using novel algorithms³³. Analyses and interpretation of the microbiome will be in the context of patient characteristics (age, sex, BMI), and use of medication, including vitamins, probiotics, and homeopathic compounds.

HPLC ion chromatography system (Metrohm AG, Herisau, Switzerland) will be used for the short chain fatty acid analysis. The concentrations of SCFA (acetic acid, propionic acid, butyric acid, isobutyric acid, valeric acid, isovaleric acid, 2-methylbutyric acid, caproic acid) will be measured with a conductivity detector. The 6.1005.200 Metrosep Organic Acids column (Metrohm AG) with 5mm particle size and dimensions of 7.8 mm by 250 mm will be used for differentiating fatty acids. The mobile phase is 5mM HNO₃ and acetonitrile v/v ratio of 98:2, respectively, with a flow rate of 0.6 ml per minute.

Fecal calprotectin levels will be measured in the collected fecal samples (baseline, mid-trial, end of intervention) using Enzyme-Linked Immuno Sorbent Assay (ELISA).

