8.4. Withdrawal of individual subjects

Subjects can leave the study at any time for any reason if they wish to do so without any consequences. The investigator can decide to withdraw a subject from the study for urgent medical reasons. If subjects leave the study, their results (blood samples, fecal samples, and questionnaires) will be used for the analyses unless the patient specifically states that we may not use the collected data and material when signing the informed consent.

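### Week-3 (T1) SCFA and microbiome results enter none of the regression models named in 10.1 and 10.2, so a patient who leaves between week 3 and week 6 adds nothing to the primary analysis

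*Protocol*

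**What the plan says.** **Collection and assay.** Protocol 8.1.1, on the main parameter: "SCFA will be measured at baseline, halfway intervention and after 6 weeks". Protocol 8.3.6, on the microbiome: "The composition and function of the gut microbiome will be analyzed prior to, mid-trial, and after the WholeFiber™ intervention using whole genome sequencing". Protocol 8.3.5 and the flow chart in 15.1 schedule feces sampling at all three visits.

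**Analysis.** Section 10 opens: "To correctly model the paired pre-post study design, we will use a linear mixed-effects model". In 10.1 the primary model is described as "modeling the fecal SCFA levels post-intervention as the dependent variable and fecal SCFA levels pre-intervention together with patient-specific intercepts" and slopes. The SCFA–microbiota model in 10.1 also has post-intervention SCFA as its outcome. The species model in 10.2 regresses post-intervention abundance on pre-intervention abundance. Section 10 mentions neither T1, mid-trial nor week 3.

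**Patients who leave.** Protocol 8.4: "If subjects leave the study, their results (blood samples, fecal samples, and questionnaires) will be used for the analyses", unless the patient has refused this. Protocol 8.6 provides replacement only for withdrawal before the intervention has started.

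**Size and expectation.** Protocol 4.4: "A sample size calculation was not performed for this study since it is an explorative study", and "inclusion of 20 participants should be sufficient". Protocol 13.1 (f) cites, from an earlier trial, "an increase of +26% in total SCFA levels was measured within two weeks after 15 g/day consumption".

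**The concern.** The primary endpoint is measured three times and modelled twice. By T1 patients have had one week at the starting amount and two at the full amount, so T1 is an on-product measurement of the primary endpoint.

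Two things follow. First, no named model describes or tests the week-3 result. Second, a patient who gives T0 and T1 samples and then leaves has no outcome value in the primary model and drops out of it. With 20 patients and no replacement after the start, each such loss counts. If the reason for leaving is related to the response, an analysis of completers alone may also be biased.

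**Working it through.** The protocol states no power, SD, effect size or dropout rate for this trial, so there is no figure of its own to reproduce. The check has four parts.

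**1. Counts.** 20 patients × 3 visits = 60 planned fecal collections, of which 20 (one third) are at T1. With post-intervention read as T2, the primary model has one outcome row per patient, and a patient without T2 has none.

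**2. Precision of T2−T0, with and without T1.** Assumptions: equal variances (SD 1), a common correlation ρ between visits of 0.3 to 0.7, and d = 0, 2 or 4 of 20 patients leaving after T1. The comparator is the paired change in completers.

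- Completers only: variance = 2(1−ρ)/(20−d).
- All three visits as outcomes, visit as a factor: variance = R/(20−d) + [2(1−ρ)−R]/20, where R = 1 − 2ρ²/(1+ρ) is the variance of T2 given T0 and T1.
- The ratio simplifies: proportional reduction in variance = (d/20) × 1/[2(1+ρ)].

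| d | ρ = 0.3 | ρ = 0.5 | ρ = 0.7 |
|---|---|---|---|
| 0 | 0% | 0% | 0% |
| 2 | 3.8% | 3.3% | 2.9% |
| 4 | 7.7% | 6.7% | 5.9% |

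Example, d = 4 and ρ = 0.5: completers 1/16 = 0.0625; all visits 0.667/16 + 0.333/20 = 0.0583; reduction 6.7%.

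For scale, the 95% CI half-width of the paired change is 0.468 SD of the difference with 20 pairs, 0.497 with 18 and 0.533 with 16. T1 recovers only part of what dropout costs.

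**3. Power for T2−T0.** Assumptions: log scale, effect ln(1.26) = 0.231, within-patient SD = √ln(1+CV²) = 0.340 at CV 35%, two-sided 5%, non-central t.

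- No leavers: SE = 0.340 × √(2/20) = 0.1075 with or without T1. Power is 53% with 19 df (paired) and 55% with 38 df (three visits). The gain comes from degrees of freedom only.
- Three leavers, within-patient information only: the variance multiplier falls from 2/17 = 0.1176 to 0.1132 (about 4%), and power goes from 46% (16 df) to 50% (35 df).

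**4. A different contrast, mean(T1,T2)−T0.** Its variance per patient is 1.5 units against 2.

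- No leavers: information ratio 2/1.5 = 1.33. Three leavers: (17/1.5 + 3/2)/(17/2) = 12.83/8.5 = 1.51.
- Power at CV 35% goes from 53% to 68%, but only if the effect is equal at weeks 3 and 6.
- If the week-3 effect were 60% of the week-6 effect on the log scale, the averaged effect would be 0.8 × 0.231 = 0.185. With SE 0.340 × √(1.5/20) = 0.0931, power is about 49%, below the 53% of plain T2−T0.

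**The case against.** **Week 6 against baseline is the stated question.** The objective concerns six weeks of use, and leaving an intermediate visit out of the primary contrast is a legitimate choice. This stands, and the fix keeps T2−T0 as primary.

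**Secondary use of T1 can be left to an analysis plan.** In general it can. Here, however, the protocol itself fixes outcome, predictor, random effects, covariates and software, and what it fixes has no place for T1. Reading post-intervention to include T1 is strained, because 8.3.6 separates mid-trial from after the intervention.

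**A reader might infer that a third of the data goes unused.** The text does not support that. Section 8.3.6 says the mid-trial microbiome will be analyzed and changes over time traced, the diversity analysis in 10.2 names no visits, and the general descriptive summaries in section 10 do not exclude T1. The omission is from the named regression models.

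**A reader might also infer that much power is lost.** The 33% and 51% information gains and the rise from 53% to 68% belong to the averaged contrast with an equal effect at both visits. The support for equality in 13.1 (f) comes from another population and intake, and 6.3 describes the microbiota response as depending on dose. Moreover, 4.4 says the trial does not aim for significance, so power is only a rough yardstick.

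**The dropout argument has limits.** No rate is given. Section 6.4 expects gastrointestinal symptoms to last two weeks at most, so patients leaving for intolerance may go before T1, and no use of T1 rescues them. Section 8.4 can be read as concerning permission to use material, not entry into the primary model. It is therefore in tension with 10.1 rather than in flat contradiction.

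**The model needs rewriting anyway.** With 20 outcome rows against 40 random effects (20 intercepts and 20 slopes), lme4 refuses to fit it, and a test fit on simulated data was refused even with random intercepts only. That is a separate defect. Repairing it does not by itself bring T1 in, so the point still has to be made.

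**Conclusion.** The point holds in a limited form. SCFA and microbiome are assayed at three visits; the SCFA, species and SCFA–microbiota models in 10.1 and 10.2 are pre-post only; and a patient leaving between weeks 3 and 6 is neither in the primary analysis nor replaced.

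For T2−T0 the gain from including T1 is nil without dropout, apart from residual degrees of freedom, and about 3–8% of the variance if 2 to 4 of 20 leave after T1. These figures rest on assumed correlations of 0.3–0.7, equal variances, an assumed CV of 35% for power, and assumed leaver counts. Keeping leavers in the model protects against bias only if their missing week-6 values are missing at random given T0 and T1.

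The main reason to change is that the primary analysis would then include the leavers' data, as 8.4 suggests, and T1 would have a defined role. The precision gain is secondary.

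**What to change.** In 10.1 and 10.2, replace the post-on-pre regressions with a repeated-measures model in which the T0, T1 and T2 values are all outcomes. Use visit as a three-level factor, because intake steps up after week 1 and a straight line over time is hard to defend, and a patient random intercept. Keep T2−T0 as the primary contrast. Include every patient with T0 and at least one later sample, and state the missing-at-random assumption. Say how T1 enters the SCFA–microbiota model.

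Optionally, report mean(T1,T2)−T0 as a supportive contrast, labelled as a different question (the average effect over weeks 3 and 6). Any precision or power claimed for it should carry the equal-effect assumption.

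The cost is wording in two sections. No visit, sample or assay is added.
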